8.3 Subsequent assessments and procedures

This section describes all proposed outcome measures and assessments in Phase 2. Data collection will be conducted face-to-face (or via telephone at 20 weeks if face-to-face data collection is problematic).

Primary outcome measures

The co-primary outcome measures will be:

i) Acceptability:

a) Participants attending >=60% sessions;

b) 'Satisfactory' ratings of therapy using the Satisfaction with Therapy and Therapist Scale-Revised (Oei et al., 2008): A 12-item self-report measure of satisfaction with therapy and satisfaction with the therapist, rated on a 5-point scale from 1 (strongly disagree) to 5 (strongly agree). There is no set definition of what constitutes "satisfactory" and so we will define this as a total score of 21 or more on the Satisfaction with Therapy subscale.

ii) Feasibility:

a) Recruitment of $\geq 80\%$ of the target sample size in a 10 month recruitment period;

b) Retention rate of >=60%.

Secondary outcome measures

The secondary outcome measures will be:

i) Acceptability:

a) Failures to recruit due to lack of acceptability of the intervention;

b) Participants dropped out due to lack of acceptability of the intervention;

c) Credibility/Expectancy Questionnaire (Devilly et al., 2000): It is important to evaluate treatment credibility/expectancy when developing a new intervention as this can have a significant impact on uptake and dropout rates. The Credibility/Expectancy Questionnaire is a 6-item self-report measure that assesses the credibility of the rationale for therapy and treatment expectancy, which will be adapted for GAD and measured immediately after the first therapy session. Four items are rated on a 9-point scale from 1 to 9 (lower scores are worse) and 2 items are scored on an 11-point scale from 0 to 100%. As the measure includes items rated on two scales, the items will be standardised and summed to form separate composite scores for credibility and expectancy.

ii) Feasibility:

a) Eligible referrals overall and in each referral subgroup (self-referral, GPs, GP list searches, Improving Access to Psychological Therapies services, and Community Mental Health Teams);

b) Eligible participants recruited;

c) Failures to recruit for reasons other than dissatisfaction with therapy (together with reasons for this);

d) Participants dropped out for reasons other than dissatisfaction with therapy (together with reasons for this);

e) ACT Treatment Integrity Coding Manual (Plumb et al., 2010): A coding system that has been developed to assess treatment integrity in ACT interventions, which has been used in previous randomised controlled trials of ACT (Twohig et al., 2010). In this coding system, the frequency and depth of coverage of major components of ACT (defusion, willingness/acceptance, creative hopelessness/workability, values and goals, committed action, general assessment of goals for treatment, symptoms and general functioning), together with overall adherence and overall therapist competence, are rated on a five-point scale from 1 (not at all) to 5 (extensively). Coding will be completed by an independent ACT therapist;

f) Adherence Checklist: A checklist of ACT components, ACT techniques, and themes discussed in each session, together with any deviations from the manual, which will be adapted from that which is currently being used in the CanACT trial (Serfaty et al., 2014). The outcome will be deviations from the manual.

iii) Patient-reported outcome measures at 0 and 20 weeks:

a) Geriatric Anxiety Inventory (Pachana et al., 2007): A 20-item "agree/disagree" self-report measure of anxiety developed specifically for older people so that it minimises somatic symptoms as these frequently overlap with physical health conditions commonly found in older people;

b) Penn State Worry Questionnaire (Meyer et al., 1990): A 16-item self-report measure of worry severity widely used in GAD, rated on a 5-point scale from 0 (not at all typical of me) to 5 (very typical of me);

c) Geriatric Depression Scale-15 (Yesavage et al., 1983): A 15-item "yes/no" self-report measure of depression developed specifically for use with older people for reasons noted above, necessary as GAD is most frequently comorbid with depression;

d) EQ-5D-5L including the VAS (EuroQol Group, 1990; Herdman et al., 2011): A 5-item self-report measure of health-related quality of life, used to calculate utility scores for quality-adjusted life years, rated on a 5-point scale from no problems to extreme problems;

e) A short modified version of the Client Service Receipt Inventory (Beecham et al., 1992; Serfaty et al., 2009): A measure of service utilization, used to calculate quality-adjusted life years. Where consent is provided, data will also be extracted from GP medical records on GP/nurse consultations, prescribing and referrals in the 20 weeks before baseline and during receipt of ACT; f) Acceptance and Action Questionnaire-II (Bond et al., 2011): A 7-item process measure of experiential avoidance or psychological inflexibility commonly used in ACT and currently being used in the CanACT trial (Serfaty et al., 2014).

Qualitative interviews

Individual qualitative interviews will be conducted with an estimated 15 participants, or until saturation is reached, after completing therapy in Phase 2 to further examine the acceptability and feasibility of the intervention. The perceived benefits and limitations of the intervention will be explored, together with any recommendations for revising the manual. Purposive sampling will be conducted on the basis of sex, socio-economic status, ethnicity, recruitment source and session attendance to explore a range of perspectives. All therapists will be interviewed to examine how the intervention was delivered in practice (e.g. treatment fidelity, ease of delivering ACT for treatment-resistant GAD in older people, difficulty of skills for participants to learn, etc).

Monitoring measures:

As a drug stabilisation period will not be included in the feasibility study, the name, dose and frequency of all psychotropic medication prescribed, and any changes to this, will be recorded during the course of the study. This information will be extracted from GP medical records, with participants' consent. This will then be included as a covariate in statistical analyses. Participants will be asked to refrain from engaging in other forms of psychotherapy during the delivery of the intervention as engaging in two types of psychotherapy concurrently may lead to conflicts in therapeutic approaches and goals. Other psychological or psychosocial interventions that participants engage in during the course of the study will be recorded, along with any interventions that participants are referred for after receiving the intervention. Evidence of any adverse effects from the intervention will also be monitored and recorded throughout the feasibility study.

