b) 'Satisfactory' ratings of therapy, defined as a total score of 21 or more on the Satisfaction with Therapy and Therapist Scale-Revised (Oei et al., 2008).

ii) Feasibility:

a) Recruitment of $\geq 80\%$ of the target sample size in a 10 month recruitment period;

b) Retention rate of $\geq=60\%$ as measured by attendance at the final follow-up assessment.

Three out of four criteria will need to be met in order for success to be demonstrated.

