Appendix 4 – Schedule of assessments

	Phase 1: Screening	Phase 1 develo	: Manual pment	Phase 2: Screening & baseline Ax		Phase 2: Intervention						Phase 2: Follow-up Ax	
Visit No	1	2	3	1	2-3	4-5	6-7	8-9	10-11	12-13	14-15	16-17	18
Day(s)	1	2	3	1	1-2	3-4	5-6	7-8	9-10	11-12	13-14	15-16	1
Window of flexibility for visits	N/A	e.g. +/- 2 weeks	e.g. +/- 2 weeks	N/A	e.g. +/- 2 weeks	e.g. +/- 2 weeks	e.g. +/- 2 weeks	e.g. +/- 2 weeks	e.g. +/- 2 weeks	e.g. +/- 2 weeks	e.g. +/- 2 weeks	e.g. +/- 2 weeks	e.g. +/- 2 weeks
Informed consent	Х			Х									
GAD-7	Х			Х									
MINI	Х			Х									
SCID	Х			Х									
SMMSE	Х			Х									
Eligibility confirmation	Х			Х									
GAI				Х									Х
PWSQ				Х									Х
GDS-15				Х									Х
EQ-5D-5L				Х									Х
CSRI				Х									Х
AAQ-II				Х									Х
STTS-R													Х
CEQ					Х								
Qualitative interview		Х	Х										Х
Intervention					ACT+	ACT+	ACT+	ACT+	ACT+	ACT+	ACT+	ACT+	
AE review	X			X	Х	Х	Х	Х	Х	Х	Х	Х	X

Note: AAQ-II = Acceptance and Action Questionnaire-II; ACT+ = Acceptance and Commitment Therapy plus usual care; AE = adverse events; Ax = assessment; CEQ = Credibility/Expectancy Questionnaire; CSRI = Client Service Receipt Inventory; GAD-7 = Generalized Anxiety Disorder-7; GAI = Geriatric Anxiety Inventory; GDS-15 = Geriatric Depression Scale-15; MINI = MINI International Neuropsychiatric Interview; PSWQ = Penn State Worry Questionnaire; SCID = Structured Clinical Interview for DSM-IV Axis II Disorders; SMMSE = Standardised Mini-Mental State Examination; STTS-R = Satisfaction with Therapy and Therapist Scale-Revised.

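### The co-primary satisfaction rating is collected face to face or by telephone with no private-completion step, so courtesy toward the study team may raise the share scoring 21 or more on the therapy subscale

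*Protocol*

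**What the plan says.** Section 8.3 covers all Phase 2 outcome measures and fixes one mode for them: "Data collection will be conducted face-to-face (or via telephone at 20 weeks if face-to-face data collection is problematic".

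One of the co-primary acceptability measures in that section is the Satisfaction with Therapy and Therapist Scale-Revised, described as "A 12-item self-report measure of satisfaction with therapy and satisfaction with the therapist". Each item scores 1 for strong disagreement up to 5 for strong agreement. Section 8.3 notes that there is no established meaning of a satisfactory rating and continues: "we will define this as a total score of 21 or more on the Satisfaction with Therapy subscale". Section 11.1 restates the criterion differently: "defined as a total score of 21 or more on the Satisfaction with Therapy and Therapist Scale-Revised". It then gives the decision rule: "Three out of four criteria will need to be met in order for success to be demonstrated".

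Appendix 4 marks the satisfaction scale only in the column "Phase 2: Follow-up Ax" (visit 18). The qualitative interview is marked in the same column. Section 8.3 says that an estimated 15 participants are interviewed after therapy, about benefits and limitations alike.

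On who collects the data, section 10.3 says only that case report forms are completed by staff on the delegation log. Section 8.3 names an independent rater for treatment integrity coding but nobody for the satisfaction rating.

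**The concern.** A satisfaction rating asks the participant to judge the therapy and the person who gave it. If it is given to, or in front of, someone connected with the project, politeness tends to push it upward. The same mode is a reasonable choice for the symptom scales, but a weaker one for a rating dichotomised at a fixed score.

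The study is open and has one arm, so no comparison group shares the upward pull. Section 11.5.2 makes the primary analysis descriptive, and no analysis plan can restore privacy after the data are collected. What is at stake is one of the four success criteria: the reported share of satisfied participants may be too high, and that share will inform the decision on a substantive trial.

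**Working it through.** **1. Is there a plan figure to reproduce?** There is none for satisfaction. The only precision statement for an acceptability criterion is in section 11.3, for attendance: 80% of 35 with a 95% interval of 0.63 to 0.92. An exact (Clopper-Pearson) interval for 28/35 is 0.631 to 0.916, which agrees. It supplies the number of completers (35) used below and nothing else.

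**2. What the sections fix and what they leave open**

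| Question | Where | Answer |
|---|---|---|
| Contact mode | 8.3 | Face to face; telephone as fallback at 20 weeks |
| Exception for the satisfaction scale | 8.3 | None |
| Type of instrument | 8.3 | Self-report, so it can be completed by hand at a visit |
| Visit | Appendix 4 | 18, same column as the interview |
| Who is interviewed | 8.3 | About 15; 15/35 = 43% of expected completers |
| Order of rating and interview | – | Not stated |
| Collector | 10.3 | Delegated staff; no role named for this scale |
| Private or sealed completion, mode recorded | – | Not stated |
| Share of participants who must be satisfied | 8.3, 11.1 | Not stated |

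**3. What the cut-off of 21 means on each reading**

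The protocol does not give the item split, so assume that 6 of the 12 items form the therapy subscale.

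- Subscale (8.3): range 6 × 1 = 6 to 6 × 5 = 30; all-neutral score 6 × 3 = 18; item mean at the cut-off 21/6 = 3.5. One extra point on three items (18 + 3 = 21) turns an all-neutral respondent into a satisfied one.
- Whole scale (11.1): range 12 to 60; all-neutral score 12 × 3 = 36; item mean at the cut-off 21/12 = 1.75. An all-neutral respondent already passes by 36 − 21 = 15 points, so courtesy hardly matters.

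The effect therefore bears on the criterion only under the subscale reading.

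**4. Illustration of sensitivity on the subscale reading (all inputs assumed)**

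With approximately normal scores and a continuity correction, the share at or above 21 is 1 − Φ((20.5 − mean − lift)/SD). Assume a private mean of 20 to 23, an SD of 3.5 to 4.5, and a lift of 0.1 to 0.3 points per item, which is 6 × 0.1 = 0.6 to 6 × 0.3 = 1.8 in total.

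| Private mean, SD | No lift | Lift 0.6 | Lift 1.8 | Gain |
|---|---|---|---|---|
| 20, 3.5 | 0.443 | 0.511 | 0.645 | 0.068 to 0.202 |
| 23, 4.5 | 0.711 | 0.755 | 0.830 | 0.044 to 0.120 |

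Over the whole assumed range the gain is 4.4 to 20.2 percentage points. Among 35 completers that is 35 × 0.044 = 1.5 to 35 × 0.202 = 7.1, or roughly 2 to 7 people. The lift is the very bias in question, so this shows how sensitive a cut-off of 21 would be and is no estimate of the bias.

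**The case against.** The best reply is that section 8.3 describes how participants are contacted, not how the form is administered. A self-report form completed by hand at a visit satisfies the protocol as written, and nothing says that items are read out or answers watched. This stands for visits. It does not cover the telephone fallback, where answers are given aloud unless a form is sent, and it leaves the visit with no stated privacy.

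A reader might infer that the rating is given to a member of the team that built the therapy. The documents do not say so. The research assistant belongs to the Project Development Group (section 13.1) and responds to distress at interviews (section 3.1), which makes this plausible, but no section names the collector of the 20-week scales. Nor does any section have the therapists collecting outcomes, and section 10.2 does not list them among those with database access.

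A reader might also infer that the rating follows a conversation praising the therapy. Only about 15 participants are interviewed, the order is open, and the interview covers limitations as well as benefits.

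Finally, a reader might conclude that acceptability is overstated or that the study could wrongly be declared a success. Neither can be shown. No size can be derived from the documents, 21 is a cut-off for the individual with no required share attached, and this mode does not affect how attendance, recruitment or retention is measured.

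It is also fair to object that routine postal return among some 35 older participants could lose co-primary data, and selectively if dissatisfied people return fewer forms. That argues for private completion at the visit, with post kept for telephone cases.

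**Conclusion.** The point holds in a limited form. The stated mode covers the co-primary satisfaction rating without any private-completion step, the rating shares a visit with the interview, and the telephone fallback is likely to mean spoken answers. Courtesy may therefore raise the share scoring 21 or more, and the planned descriptive analysis cannot remove it.

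The conclusion rests on the subscale reading of the cut-off in section 8.3; on the whole-scale wording in section 11.1 nearly everyone would pass regardless. That contradiction has to be settled in its own right. The 4 to 20 percentage points follow from an assumed item split, mean, SD and lift, and should not be quoted as an expected bias. A changed success verdict is not demonstrated. This is a cheap improvement to a stated design choice and does not invalidate the criterion.

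**What to change.** In section 8.3, add that:

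- the participant completes the satisfaction scale privately at the 20-week visit, before any qualitative interview, and hands it over in a sealed envelope, having been told that therapists and interviewers will not see it;
- for telephone follow-up only, the form is posted with a reply envelope;
- the mode of completion and any assistance are recorded, and the result is reported by mode.

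Reconcile sections 8.3 and 11.1 so that both state whether 21 applies to the therapy subscale or to the whole scale.

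The cost is a short addition to 8.3, a wording correction, envelopes and some postage. The downside is a few incomplete forms, mainly among those followed up by telephone. Routine postal return and a separate uninvolved helper are not needed: the first risks missing co-primary data and the second adds staffing.

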8.4 Discontinuation/withdrawal of participants

In consenting to participate in the study, participants are consenting to intervention, assessments, follow-up and data collection. A participant may be withdrawn from the study whenever continued participation is no longer in the participant's best interests, but the reasons for doing so must be recorded (whenever possible). Reasons for discontinuing the study may include:

- active suicidal ideation with intent and plans;
- illness that may exclude the possibility of engagement in the intervention;
- a person withdrawing consent or losing the capacity to consent to participate in the study.

The decision to withdraw a participant from treatment will be recorded in the Case Report Form (CRF) and Investigator Site Files. If a participant explicitly states they do not wish to contribute further data to the study their decision must be respected and recorded in the CRF.

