3.1 Assessment and management of risk

Information sheets will provide participants with information about the possible benefits and risks of taking part in the study. Participants will be given the opportunity to discuss this with the researcher prior to consenting to the study.

Risk: Participants will remain under the care of their GP/consultant psychiatrist/care coordinator for the duration of the open uncontrolled feasibility study. Risk of harm to self or others will be monitored throughout the study. If suicidal ideation without intent is expressed at any point then the participant's GP/consultant psychiatrist/care coordinator will be contacted and the participant will continue to be monitored weekly. If suicidal ideation with active intent is expressed at any point then the participant's GP/consultant psychiatrist/care coordinator will be referred for urgent psychiatric assessment. The decision as to whether the participant should be withdrawn from the study will depend on the outcome of this assessment, and in full discussion with the participant and clinical team.

Inadequate treatment response: If a participant remains moderately to severely anxious or depressed after receiving ACT (as indicated by a score of >8 on the Geriatric Depression Scale or >11 on the Geriatric Anxiety Inventory) then this will be discussed

with the participant and appropriate action will be taken (e.g. their GP/consultant psychiatrist/care coordinator will be contacted and the participant will be referred for further psychotherapy or medication review).

Potential distress: Any distress experienced during qualitative interviews will be identified and responded to by the research assistant, under the supervision of the Chief Investigator. Evidence of any adverse effects from the ACT intervention will be monitored throughout the feasibility study. Reasons for withdrawing participants from the ACT intervention (e.g. if participants require immediate inpatient treatment) will be discussed with the Project Management Group prior to the commencement of the feasibility study. Anyone experiencing an increase in distress will be assessed for risk and standard operating procedures will ensure safety is respected. New reports of suicidal behaviour during the ACT intervention will be reported as Serious Adverse Events.

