6.2 Exclusion criteria

1. Diagnosis of dementia;

2. Standardised Mini-Mental State Examination (Molloy et al., 1991) score of <25;

3. Currently receiving ongoing psychotherapy or who are unwilling to refrain from engaging in other forms of psychotherapy during the receipt of ACT;

4. Suicidal ideation with active intent for whom an inpatient admission would be more appropriate;

5. Other medical or psychosocial factors that could compromise full study participation such as imminently life-limiting illness or severe sensory deficits (e.g. blindness);

6. Intellectual disabilities.

It is common to include a psychotropic drug stabilisation period (e.g. a stable dose for at least two months) as one of the inclusion criteria in psychotherapy studies to allow for spontaneous recovery, and to control for the potential confound of pharmacotherapy on mental wellbeing. However, this will not be included in the current feasibility study for two reasons. First, spontaneous recovery in those who have not responded to Steps 1-3 of the stepped care approach for GAD is unlikely. Secondly, it is likely that a drug stabilisation period would have a significantly negative impact on recruitment as many potential participants would either be ineligible to take part or unwilling to wait for drug stabilisation to occur before receiving psychotherapy. Service users are frequently referred to Community Mental Health Teams (CMHTs) for medication reviews, which usually entails switching to

another drug, adding in another drug, or changing drug doses, and so it can take a number of months before a stable dose is achieved. Instead of including a psychotropic drug stabilisation period, all drug use will be monitored during the course of therapy, and will be accounted for in subsequent data analyses.

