6.4 Informed consent

Participants would be expected to be able to provide informed consent for participation, provided that appropriate time and care has been taken by the Band 5 clinician, research nurse or research assistant to explain the research, and they had sufficient time to make a decision. It will be explained that participants are under no obligation to enter the study and that they can withdraw at any time, without having to give a reason and without their subsequent care being affected. It will be made clear to participants that no

disadvantage will accrue if they choose not to participate in the study. It is not expected that participants will lose the capacity to provide informed consent during the course of the study. If they do, then they will be withdrawn from the study. The initial giving of informed consent provides a clear indication of the person's likely perspective on continuing at this point. Current guidance from the British Psychological Society on evaluation of capacity when seeking consent will be followed, which is regarded as a continuing process rather than a one-off decision. Willingness to continue participating will be continually checked through discussion with participants during the study.

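### Section 8.4 allows illness that only prevents engagement in ACT to end participation in the whole study, and no passage states that people who stop ACT are still followed up at 20 weeks

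*Protocol*

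**What the plan says.** Section 8.4 allows a participant to be withdrawn from the study when staying in it no longer serves that person's best interests. It then gives examples of reasons for discontinuing the study, one of which is "illness that may exclude the possibility of engagement in the intervention". The next paragraph moves to a different event: "The decision to withdraw a participant from treatment will be recorded in the Case Report Form (CRF) and Investigator Site Files". It says how that event is recorded, but not what happens to follow-up. The section also says that on entry "participants are consenting to intervention, assessments, follow-up and data collection", and that an explicit refusal to give further data must be respected.

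Other sections bear on the point:

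- Section 3.1 treats the two events as separate decisions. One sentence concerns "Reasons for withdrawing participants from the ACT intervention (e.g. if participants require immediate inpatient treatment"), and leaves these reasons for the Project Management Group to discuss before the feasibility study starts. Another, on suicidal ideation with active intent, says "The decision as to whether the participant should be withdrawn from the study will depend on the outcome of this assessment".
- Section 6.4, on loss of capacity to consent: "If they do, then they will be withdrawn from the study".
- Section 8.3 allows outcome data to be collected "via telephone at 20 weeks if face-to-face data collection is problematic".
- Section 11.1 defines retention by attendance at the final follow-up assessment, sets the criterion at 60% or more, and requires three of the four criteria for success.
- Appendix 4 schedules the Satisfaction with Therapy and Therapist Scale-Revised (STTS-R) only at visit 18, the follow-up assessment.

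**The concern.** The illness example describes a barrier to therapy, yet it is listed as a reason to leave the study. ACT is planned as 16 one-hour sessions; the follow-up is a single assessment that can be done by telephone. Some illnesses will rule out the first and not the second. Because 8.4 does not separate stopping treatment from leaving the study, site staff could reasonably take a person in this position out of both.

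A person withdrawn in this way counts as not retained, although the cause lies in the treatment and not in the assessment. That person gives no STTS-R score, no 20-week patient-reported outcomes and no 20-week Client Service Receipt Inventory, which section 11.5.6 uses for costs. The loss is related to health, so it cannot be assumed unrelated to outcome. The study is also meant to supply design parameters for a later trial, and a retention figure that mixes stopping therapy with loss to assessment serves that purpose less well. An analysis plan cannot mend this, because it cannot recover an assessment that was never offered.

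**Working it through.** **The protocol's own figures.** Section 11.3 starts from 35 participants and a 12.5% loss: 35 / (1 − 0.125) = 40, as stated. The exact 95% interval for 28/35 (80% session attendance) is 0.631 to 0.916, which matches the stated 0.63 to 0.92. Planned follow-up is therefore 35/40 = 87.5%.

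**Reading the sections together.** Sections 3.1, 6.4, 8.3, 8.4, 11.1 and 11.5.4 and Appendices 1 and 4 were checked for a rule on follow-up after ACT stops. None states one. Three features imply that follow-up goes on: consent lists intervention, assessments and follow-up as separate items; refusal of further data has to be explicit; and 3.1 keeps the two kinds of withdrawal apart. The illness example in 8.4 points the other way.

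**Effect on retention.** The protocol gives no number of people expected to stop ACT. Let k be the number withdrawn for illness who could have been assessed, with k = 1 to 5 as an assumption. Each one changes retention by 1/40 = 2.5 points.

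- If they are among the 5 planned losses, observed retention is 35/40 = 87.5%, where (35 + 1)/40 = 90.0% to (35 + 5)/40 = 100% was reachable.
- If they come on top of the 5 planned losses, retention is (35 − 1)/40 = 85.0% to (35 − 5)/40 = 75.0%.
- The criterion is still met after 11 extra withdrawals, (35 − 11)/40 = 60.0%, and fails at 12, (35 − 12)/40 = 57.5%.

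**Effect on before-after change.** Suppose the k people would have improved by d less than the others, with d = 0.5 to 1.0 SD (assumption), and that other losses are random. The mean over all 40 is then lower than the observed mean by k × d / 40:

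- smallest case: 1 × 0.5 / 40 = 0.0125 SD;
- largest case: 5 × 1.0 / 40 = 0.125 SD.

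The 95% half-width is 1.96/√35 = 0.331 SD with 35 people and 1.96/√30 = 0.358 SD with 30. The illustrated bias is below it throughout. If the k people did no worse than the others, there is no bias.

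**Effect on satisfaction.** Assume 28 of 35 (80%) score as satisfied; the protocol gives no expected rate. Recovering one person gives 28/36 = 77.8% to 29/36 = 80.6%. Recovering five gives 28/40 = 70.0% to 33/40 = 82.5%. The ranges lie on both sides of 80%.

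**The case against.** The strongest reply is that this is a matter of wording with little weight. The illness reason is an example under a best-interests test, and someone who can answer questions by telephone does not plainly meet that test. The default already leans towards continued follow-up, and the Project Management Group was to discuss reasons for ACT withdrawal before Phase 2. Section 6.2 excludes people with "Other medical or psychosocial factors that could compromise full study participation", which removes some cases at entry, and some who fall ill later could not be assessed in any case. Dropout reasons are a planned outcome, so the loss would be visible. Section 11.5.3 adjusts for baseline severity, comorbidity, cognition and medication, and 11.5.4 relies on a missing-at-random model, so part of the illustrated bias may be absorbed. All of this stands, and it keeps the point small. It does not supply the missing rule: the Project Management Group sentence concerns reasons for withdrawal, not follow-up afterwards.

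A reader might infer three stronger things that the documents do not support:

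- That 8.4 forces ill participants out. It is permissive throughout.
- That everyone who stops ACT is lost. On that assumption, with 87.5% attendance among the rest, retention would be (40 − 12) × 0.875 / 40 = 61.3% for 12 stoppers and (40 − 16) × 0.875 / 40 = 52.5% for 16. But the disputed reason covers illness only, no passage removes a person merely for stopping ACT, and the sum treats none of the planned 12.5% loss as ACT stoppers.
- That the satisfaction result is shown to be tilted favourably. The direction depends on what the missing people would have answered. Moreover, the protocol sets a score of 21 or more for each person but no percentage for the group, so the illustrated rates have no threshold to be compared with.

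**Conclusion.** The point holds in a limited form. Section 8.4 lists illness that prevents engagement in ACT as a permitted, discretionary reason to leave the whole study, although such a person may still be able to complete the 20-week assessment. Continued follow-up after ACT is implied but not stated. What is at risk is an avoidable, health-related loss of 20-week data: 2.5 retention points, one STTS-R score, one set of patient-reported outcomes and one service-use record for each person.

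The number affected is unknown and probably small; k = 1 to 5 and d = 0.5 to 1.0 SD are assumptions, not estimates. Neither the 60% retention criterion nor the three-of-four rule is likely to change, and before-after change is a secondary, descriptive outcome. This is a cheap improvement, not a threat to the study's conclusions.

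**What to change.** In section 8.4, separate two events:

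- (a) stopping ACT, for any reason including illness;
- (b) leaving the study, limited to withdrawn consent, lost capacity (as in 6.4), or a clinical judgement that assessment itself is against the participant's interests, for example after the psychiatric assessment described in 3.1.

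Move the illness reason under (a) and add this sentence: *Anyone who stops ACT is still invited to the 20-week assessment, by telephone if needed, unless they decline.*

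The sample size, the success criteria, the clinical discretion to stop therapy and the right to refuse further data stay as they are. The cost is a few lines in 8.4, matching wording in the CRF and information sheet, and a few extra telephone assessments within the planned 40.
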